2.7 Statistical Analysis and Sample Size Justification**A. Blinded Data Analysis:**

The investigator will be responsible for overall analysis of the data with assistance from Respiratory Motion staff in analysis of RVM data. The study will be double blinded with no knowledge of drug vs. placebo administration by investigator, clinical care providers or researchers performing the primary data analysis. A patient can be unblinded on an urgent basis if it is deemed necessary for the clinical care of the patient.

Study medication (sugammadex and placebo) will be prepared by the institutional pharmacy, and will be dispensed to the investigative team member according to the patient group assignment. The site study coordinator will call the pharmacy and alert them once a patient is enrolled in the study. The drug (sugammadex or placebo) will be prepared by the Pharmacy personnel according to the randomization sequence. The clinician administering the drug (sugammadex or placebo) will be blinded to the drug identity.

The investigators will be responsible for analyzing the study data, and the analysts will be blinded to patients' group assignment during the execution of the study. For the purpose of the final analysis, the official clinical database will not be unblinded until medical/scientific review has been completed and the investigators have been assured that the data are complete.

B. Statistical Analysis:

- a. Using Fisher exact test, we will compare across the two groups the incidence of:
 - i. Sustained MV<80%MV_{PRED} for at least 1 minute in the first 15-30 minutes after arrival in PACU
 - ii. Sustained MV<40% MV_{PRED} for more than 10 contiguous minutes of the last 30 minutes prior to PACU discharge
 - iii.. Sustained MV<40%MV_{PRED} for at least 2 minutes after opioid administration (amongst patients receiving opioids in the PACU)
 - iv. Sustained MV<40%MV_{PRED} for at least 2 minutes in the absence of opioids (amongst patients w/o opioids in the PACU)
 - v. Sustained MV<40%MV_{PRED} for at least 2 minutes after opioid administration (amongst patients receiving opioids in the PACU) when corrected for PACU LOS
 - vi. Sustained MV<40%MV_{PRED} for at least 2 minutes in the absence of opioids (amongst patients w/o opioids in the PACU when corrected for PACU LOS
 - vii. Adverse events, including:
 - 1. Respiratory complications (O₂ desaturation, atelectasis, respiratory status requiring advanced monitoring, etc.)
 - 2. Respiratory interventions (O₂ administration, CPAP, BiPAP, medications, etc.)
 - 3. ICU or step-down unit transfer
 - viii. Normal TOF ratio (>0.90) at equivalent time points in the PACU (e.g. on arrival, at discharge, etc...)
- b. Using 2-sample t-tests we will compare:
 - i. Average MV during the 15-30 minutes after arrival at the PACU
 - ii. Average MV during the 30 minutes prior to the time cleared for PACU discharge
 - iii. Average LOS in the PACU
 - iv. Average pain scores
 - v. Average total opioid dose (morphine equivalents) in the PACU

	
c. Using paired t-tests we will compare:
 
 i. MV, TV, and RR measurements before and after sugammadex administration 
d. We will perform sensitivity and specificity analysis to evaluate the ability of sugammadex to:
 
 i. Decrease respiratory complications (O_2 desaturation, atelectasis, respiratory status requiring advanced monitoring, etc.) ii. Decrease the need for respiratory interventions (O_2 administration, CPAP, BiPAP, medications, etc.) iii. Decrease transfers to step-down or ICU iv. Decrease LOS in PACU v. Increase MV in the PACU at the following time points: 
 1. On arrival 2. After opioids 3. At discharge 
e. We will perform multi-factor Analysis of Variance (MFANOVA) with dependent variables: "sustained MV<40% MV_{PRED} for at least 2 minutes", "Adverse event", PACU LOS, etc... as defined in each hypothesis, based on demographics to demonstrate group uniformity.
 
f. We will use Pearson correlations and linear regressions, without regard to treatment group to compare:
 
 i. MV measurements and TOF ratios ii. MV measurements and total opioid dose iii. Pain scores and total opioid dose iv. MV measurements and pain scores 
C. Multiplicity: For the purposes of this work, we will treat Hypothesis A1 as a primary objective and A2 as a key secondary. We will consider $p<0.05$ to be statistically significant for the primary objective and this result will be the main outcome of our study. We will test the key secondary objective (at $p<0.05$ significance level) only if we have achieved significance with the primary.
 
We will continue with testing the remaining secondary hypotheses only if we have significant results from the primary and the key secondary. For each additional secondary hypothesis, we will calculate statistical significance both with and without Hochberg correction.¹⁴ If we discover marginally significant effects in any of the remaining hypotheses, we will propose additional studies powered and geared towards specifically addressing said hypotheses.

--	--

D. Power/Sample Size:

Considering the study in general, the incidence of residual neuromuscular block in the PACU is estimated to be 35%.¹¹ Based upon a sample size of n=92 patients per group, this study has 80% power to detect a 5% difference between groups in incidence of residual block; this calculation is based on a standard deviation of 12%. We would need 100 patients per group in order to be conservative to observe this effect. However, more specific calculations related to our primary and key secondary hypotheses described below suggest we would need 150 patients per group to ensure we can adequately power these hypotheses.

(1) Low MV on arrival at the PACU. We will be comparing absolute measurements of MV as well as incidences of MV<80% across the two groups. Since comparisons of incidences usually requires more data, we are basing our sample size calculations on the incidence comparison.

Previous data suggest that as many as 33% of patients arrive in the PACU with MV<80% MV_{PRED}. We anticipate that in a group of similar patients receiving sugammadex at the end of surgery, the prevalence of MV<80% MV_{PRED} will decrease significantly, by approximately 18% ($\Delta p = 0.18$). To demonstrate this reduction with 80% power ($Z_\beta = 0.84$) at a $p < 0.05$ level ($Z_{\alpha/2} = 1.96$), the required sample size (assuming a large patient population) for each of the two groups (with and w/o sugammadex) can be calculated as follows:

$$n = \frac{2 \cdot \bar{p} \cdot (1 - \bar{p}) \cdot (Z_\beta + Z_{\alpha/2})^2}{(\Delta p)^2} = 88.3$$

where $\bar{p} = \frac{p_1 + p_2}{2}$ is the average incidence in the two groups and $\Delta p = |p_1 - p_2|$ is the difference in the incidence of low MV across the two groups.

(2) Low MV at discharge from the PACU. Similarly with the PACU arrival, at PACU discharge we will compare both MV measurements as well as the incidence of Low MV and will calculate our sample size based on the incidence comparison

Previous data suggest that around 22% of patients leave the PACU

	
with MV<40% MV_{PRED} and we anticipate that in a group of similar patients receiving sugammadex at the end of surgery, the prevalence of MV<40%MV_{PRED} will decrease in half by approximately 11% ($\Delta p = 0.11$). To demonstrate this reduction with 80% power ($Z_\beta = 0.84$) at a $p<0.05$ level in a single-sided test ($Z_{\alpha/2} = 1.645$), the required sample size (assuming a large patient population) for each of the two groups (with and w/o sugammadex) can be calculated as follows:
 $n = \frac{2 \cdot \bar{p} \cdot (1 - \bar{p}) \cdot (Z_\beta + Z_{\alpha/2})^2}{(\Delta p)^2} = 143.2$ 
where $\bar{p} = \frac{p_1 + p_2}{2}$ is the average incidence in the two groups and $\Delta p = p_1 - p_2$ is the difference in the incidence of across the two groups. Hence, to adequately power our key secondary hypothesis, we plan on recruiting 300 patients (150 in each group).

2.8 Specific Drug Supply Requirements	
All drugs used in the course of providing medical care for the 300 patients will be supplied by the institutions participating in this protocol, with the exception of the investigated drug, sugammadex. A request will be made to the sponsoring company, Merck, to supply the sugammadex necessary for the 150 patients enrolled in the sugammadex study arm.
 
Institutional pharmacies will be responsible for dispensing the test drugs (sugammadex and placebo) in a blinded fashion, based on the study group assignment. The test drugs (sugammadex and placebo) will be packaged and labeled by the institutional pharmacy in a blinded fashion.

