2.5 Study Procedures

	
which may decrease the incidence of residual neuromuscular block.)
 
 1) The ExSpirom will be placed on the patients' chest prior to extubation. ExSpirom data will be collected starting prior to tracheal extubation, during transport from OR to PACU, and in PACU. 2) Patient care staff will be blinded to the ExSpirom numerical and trending data for MV, TV and RR, but the respiratory trace will be displayed to demonstrate that the ExSpirom is functioning. Of note, the gain on the trace is variable so the size of the breath visualized on the screen is not correlated to the volume of the breath. This will maintain blinding of the patient care staff. 3) TOF Monitoring with an objective monitor (TOF-Watch or StimPod) will be used in all patients once the decision to extubate the patients' trachea is made. The monitoring will continue in the PACU until full recovery (TOF=1.0) is documented. Monitoring will be performed as per usual clinical routine via surface ECG electrodes. In the PACU, the current amplitude will be decreased to 30-40 mA, current intensities that are used routinely for patient care in other centers and that do not result in patient discomfort. 4) Patient care staff will be blinded to TOF data. Only the investigator assigned to the PACU data retrieval will know the results of TOF Monitoring. 5) Patient care should follow standard hospital protocol. 6) Physiologic monitoring and clinical assessment data will be recorded as per standard protocol in the PACU. 7) All other therapies and medications including oxygen, CPAP, opioids and sedatives will be delivered in accordance with standard of care. 8) Doses and times of all medications (such as opioids, sedatives, etc.) or respiratory interventions (such as albuterol, respiratory treatment, suctioning, high flow oxygen, CPAP, BiPAP, etc.) will be recorded throughout the entire perioperative period (pre-op, OR, PACU). 9) Pain scores based on a standard analog scale (1-10) will be recorded. These will be obtained per standard clinical practice. 10) Arterial or venous blood gas values and Chest x-rays taken in the OR or PACU will be recorded when obtained as part of standard care. 
B. Study Procedures
 
 1) Screening and Recruitment: Study personnel will review the surgery schedule to identify appropriate and eligible patients. Eligible
--	--

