	
patients will be informed about the study and the study will be explained to them. They will be able to ask questions. If they would like to participate, written informed consent will be obtained. Recruitment at Mayo Clinic site will be conducted by Investigators on the day of surgery. Patients will be identified and approached before they are taken to the preoperative area. A private room located near the surgical area will be used for consenting of prospective participants. Family and/or friends will be allowed to remain with a patient during the consenting process. Patients usually arrive approximately 2 hours prior to their scheduled surgery time, which will be adequate time to discuss the study and allow patients to make an informed decision whether or not to participate in this research study.
 
2) Randomization:
 
Patients will be randomized to one of two groups: administration of sugammadex (n=150) vs. placebo (n=150) prior to tracheal extubation in the OR.
 
3) Prior to Procedure (in the OR or preoperative area):
 
 i. For RVM monitoring, ExSpiron PadSet will be placed on the patient's thorax (see Appendix A for placement instructions). Deviations from standard placement will be documented. Once in the OR the ExSpiron will be connected and the ExSpiron will be synchronized to the ventilator. ii. For TOF monitoring, skin ECG electrodes will be placed along the ulnar nerve on the volar forearm, as per routine clinical protocol. Visual or tactile intraoperative monitoring of neuromuscular block level will be performed according to the clinicians' usual routine. At the end of surgery, once the clinician has determined that recovery of neuromuscular block is adequate (after administration of standard of care reversal agents) for maintenance of spontaneous ventilation, the TOF will be determined objectively (it will be measured with the currently available monitor, TOF-Watch or StimPod), and then the patient's trachea will be extubated, as per usual clinical routine. In 150 of the 300 patients, a dose of sugammadex (2 mg/kg) will be administered, and then routine TOF measurements will be made in the PACU. 
4) Operating Room (OR):
 
 a. Record all medications (dose, route, time)
--	--

- b. Record surgery start and end times
- c. Record position changes
- d. Record intubation and extubation times

5) Recovery Room (PACU):

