	
become available from the study that could affect a subject's willingness to participate. No new information of clinical relevance to the subject is expected from this study. Therefore no new information will be given to the patient.
 
 i. Payment: The participants will not be compensated for their participation in the study. j. Payment for a research-related injury: This is a minimal risk study. There are no plans to provide other compensation. If a participant is injured during this study, the study doctor will discuss the available medical treatment options with the subject. 
12) Outcome: The primary outcome of this study is evaluation of the effects of sugammadex on the incidence of respiration complications postoperatively.

2.6 Study Duration	We anticipate that we will recruit the planned number of patients (n=300) at the two centers (UTHealth and Mayo Clinic) within 6 months of IRB approval and receipt of all necessary study materials and medications.

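### Unadjusted Fisher tests give up some power for the key secondary; a prespecified analysis adjusted for site and pre-dose TOF would recover part of it

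*Combined protocol and SAP*

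**What the plan says.** **The tests.** Section 2.7 B.a opens: "Using Fisher exact test, we will compare across the two groups the incidence of". Item i is the binary A1 endpoint (MV below 80% of predicted, 15-30 minutes after PACU arrival). Item ii is the binary A2 endpoint (MV below 40% of predicted before discharge). The matching comparisons of mean MV in 2.7 B.b are plain two-sample t-tests.

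**Their standing.** Section 2.7 C states that "we will treat Hypothesis A1 as a primary objective and A2 as a key secondary". It adds: "We will test the key secondary objective (at $p<0.05$ significance level) only if we have achieved significance with the primary". The other secondary hypotheses are tested only if both succeed.

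**Baseline information.** Section 2.5 A item 3 says: "TOF Monitoring with an objective monitor (TOF-Watch or StimPod) will be used in all patients once the decision to extubate". Section 2.5 B.3.ii says that, after standard reversal and before extubation, "the TOF will be determined objectively". Section 2.6 plans recruitment "at the two centers (UTHealth and Mayo Clinic"), and Section 2.5 A leaves anaesthetic management to the usual routine at the two institutions. The randomization paragraph mentions no stratification.

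**What the other analyses do.** The multi-factor ANOVA (2.7 B.e) is based on demographics, to show that the groups are alike. The regressions of MV on TOF (2.7 B.f) ignore treatment group. Neither adjusts the A1 or A2 comparison for site or pre-dose TOF.

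**The concern.** The plan's rationale is that residual block leads to respiratory depression, and Hypothesis I expects lower MV to go with lower TOF. A TOF reading taken just before the study drug is therefore the obvious prognostic baseline variable. Leaving it and site out of the main tests means that chance imbalance stays in the comparison and any precision they could give is lost. Choosing Fisher's test on top of that costs power through conservatism.

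A2 sets the sample size of 300 and gates every later claim. If it misses significance for want of a few points of power, the plan stops formal testing there, whatever the data on length of stay, complications or TOF show.

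**Working it through.** **1. The plan's own sizes.** Section 2.7 D uses n = 2·p̄(1−p̄)(Zβ+Zα)²/Δp² per group.

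- Primary, 33% vs 15%, Z = 1.96: 2 × 0.24 × 0.76 × (0.84+1.96)² / 0.18² = 0.3648 × 7.84 / 0.0324 = 88.27. The plan states 88.3.
- Key secondary, 22% vs 11%, Z = 1.645: 2 × 0.165 × 0.835 × (0.84+1.645)² / 0.11² = 0.27555 × 6.175 / 0.0121 = 140.6. The plan states 143.2, which is 1.8% higher.
- Key secondary with Z = 1.96: 0.27555 × 7.84 / 0.0121 = 178.5.

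The formula is a normal approximation for an unadjusted comparison, not for Fisher's test. The sizing text calls the A2 test one-sided ("level in a single-sided test ($Z_{\alpha/2} = 1.645"), while the testing rule in 2.7 C gives no side.

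**2. Exact power at 150 per group.** Power is the sum, over all pairs of event counts, of the two binomial probabilities multiplied together, counting only pairs where the test rejects at 0.05.

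| Comparison | Fisher | Unadjusted chi-square |
|---|---|---|
| A2, 22% vs 11%, two-sided | 68.2% | 73.7% |
| A2, 22% vs 11%, one-sided | 79.0% | 82.9% |
| A1, 33% vs 15%, two-sided | 94.8% | 96.0% |

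At a common rate of 16.5%, the midpoint of 22% and 11%, the actual two-sided size of Fisher's test is 3.4%. For A2, leaving Fisher is worth 73.7 − 68.2 = 5.5 points two-sided and 82.9 − 79.0 = 3.9 points one-sided, before any covariate is used.

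**3. Adding TOF as a stratum (A2, two-sided, simulated).** The documents give neither the share of patients with TOF below 0.90 before dosing nor how that reading relates to MV below 40% at discharge. Both are assumed here: the share is set at 38%, and the placebo risks are varied so that they average about 22% (for example 0.62 × 16% + 0.38 × 32% = 22.1%). The Mantel-Haenszel statistic sums observed minus expected events over strata and divides by the square root of the summed hypergeometric variances.

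| Placebo risk, TOF ≥0.90 / <0.90 | Stratified test, risk halved in both strata | Stratified test, benefit only in TOF <0.90 |
|---|---|---|
| 22% / 22% | 73% | not applicable |
| 16% / 32% | 75% | 73% |
| 10% / 42% | 78% | 76% |
| 5% / 50% | 82% | 81% |

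The unstratified Mantel-Haenszel test gives about 74%, so TOF itself adds from nothing to 82 − 74 = 8 points. Simulated type I error of the stratified test was 4.6-5.0%. One-sided, the stratified test gives 83-89%.

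**4. The alternative estimator.** A standardised risk difference from logistic regression on one continuous covariate gave, two-sided, 73-74% (no association), 75-76% (AUC 0.63), 79-80% (AUC 0.75) and 83-84% (AUC 0.82). If the covariate predicts outcome only on placebo, the range is 73-77%.

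**5. Site.** The documents give no difference in outcome between the centres, so no gain can be computed.

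**6. Is the TOF reading pre-dose?** Section 2.5 A starts objective TOF at the extubation decision and gives the study drug at the same trigger, without ordering the two. The opening of Section 2.5 A and the randomization paragraph put the drug before extubation. The primary objective in Section 2 and Hypothesis A in 2.1 put it after. A reading before extubation is therefore not guaranteed to be a reading before the drug.

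**The case against.** An unadjusted Fisher test is valid, so this is a matter of efficiency and not an error. That stands.

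Most of the certain gain comes from dropping Fisher, not from TOF or site. That also stands: about 5 points two-sided for the test, then 0 to 8 for TOF. If sugammadex helps mainly patients with residual block, TOF modifies the effect as well as predicting outcome, and the gain shrinks to little or nothing except under a strong association. Even so, the stratified test exceeded Fisher in every 22% vs 11% scenario run.

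Much of the apparent distance from 80% for A2 is unresolved sidedness. One-sided, Fisher already gives 79.0%. This stands, and it is why the side of the test must be stated alongside any power figure.

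A reader might also infer three stronger things that the documents do not support:

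- **That the primary is short of power.** It needs 88 per group and has 150.
- **That 35-40% of patients have residual block at dosing.** The 35% in Section 2.7 D is a PACU rate. The figure of up to 40% in Section 2.2 C has no time point. Neither describes patients already judged ready for extubation after reversal.
- **That adjustment restores 80% two-sided power.** It does so only if pre-dose TOF is a fairly strong predictor, which is not shown.

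**Conclusion.** The point holds as a modest efficiency gain for A2. Under the plan's own 22% vs 11% at 150 per group, a less conservative test adds 5.5 points two-sided or 3.9 one-sided. Stratifying by pre-dose TOF adds roughly 0 to 8 more (two-sided), resting on an assumed 38% prevalence and assumed associations. For the primary the change is small, because power is already about 95%. Site is worth including because usual care is set locally, but no power gain can be claimed for it.

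The TOF part is conditional. If some readings follow the injection, TOF is partly an outcome of treatment, and adjusting for it could remove part of the effect being tested. The documents do not yet exclude that.

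**What to change.** Before unblinding, amend Section 2.7 B and C so that:

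- A1 and A2 are tested with a Mantel-Haenszel test stratified by site and objective TOF (<0.90 / ≥0.90). A standardised risk difference from logistic regression with the same covariates would also serve.
- The adjusted risk difference is reported with its 95% CI.
- Patients without a usable TOF reading form a missing category.
- The sidedness of the A2 test is stated.
- Fisher's test is kept as a sensitivity analysis.

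In Section 2.5, state when the objective TOF is read relative to the study-drug injection, and record both times. Use TOF as a covariate only where the reading is recorded before the injection; otherwise adjust for site alone. The sections that place the drug before extubation and those that place it after must be reconciled.

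The cost is SAP wording, a missing-data rule and a short protocol clarification. Two sites by two TOF levels make four strata, or six with the missing category. No additional patients or measurements are needed if the planned TOF reading is already taken before dosing.

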Randomized Double---Blinded, Controlled
Trial to Compare the Effectiveness of
Sugammadex vs. Placebo to Prevent
Residual Neuromuscular Block in the Post---
Anesthesia Care Unit as Evaluated with a
Non---Invasive Respiratory Volume Monitor

NCT02728726

6/29/2017

f

Merck Investigator Studies Program (MISP) Protocol Template

Requirements for Submitting a Full Proposal

Section #1 - MISP Protocol Identification

Study Title:	Randomized Double-Blinded, Controlled Trial to Compare the Effectiveness of Sugammadex vs. Placebo to Prevent Residual Neuromuscular Block in the Post-Anesthesia Care Unit as Evaluated with a Non-Invasive Respiratory Volume Monitor
Request Date:	Protocol Version date 6/29/17
Institution Name:	Mayo Clinic, Jacksonville University of Texas - UT Health, Houston
Investigator Contact Information:	J. [name] Assistant Professor of Anesthesiology Department of Anesthesiology Mayo Clinic [name] O: [contact] E: [contact] [name] The University of Texas, UTHealth Department of Anesthesiology [name] [REDACTED] [REDACTED]

Section #2- Core Protocol

The Primary objective of this study is to determine whether patients who receive sugammadex immediately after tracheal extubation will exhibit a decrease in the incidence of postoperative residual paralysis and an associated decrease in the incidence of postoperative respiratory depression (which can precede critical respiratory events, CRE).

The Secondary objectives are to: a) determine whether patients receiving sugammadex will have a normal TOF ratio (>0.90) indicative of full neuromuscular recovery in the PACU; and b) to improve patient safety by documenting whether postoperative respiratory depression (decreased MV below 80% and 40% of predicted MV as assessed by a Respiratory Volume Monitor) is due to opioid administration vs. postoperative residual neuromuscular block (by comparing postoperative VAS scores and total opioid administered).

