2.1 Objectives & Hypotheses

Hypotheses:

- A. After routine care and reversal of neuromuscular block as per usual clinical routine, and after tracheal extubation, surgical patients randomized to receive sugammadex vs. placebo in the OR will:
 - 1) have a lower incidence of "Decreased MV" [MV <80% MV predicted (MV_{PRED}) based on BSA] as well as lower average MV sustained at 15-30 minutes after PACU arrival than placebo patients
 - 2) have a lower incidence of "Low MV" as well as lower average MV at PACU discharge. An instance of "low MV" occurs when the measured MV is <40% MV predicted (MVPRED) based on BSA, for any contiguous 10 minutes in the 30 minutes leading up to PACU discharge.
- B. A smaller fraction of patients in the sugammadex group than in the placebo group spend more than 2 minutes in the PACU with a sustained "Low MV."
- C. A smaller fraction of patients in the sugammadex group than in the placebo group spend more than 2 minutes in the PACU with a sustained "Low MV" when corrected for PACU length-of-stay (LOS).
- D. The average %MV predicted is greater in the sugammadex group than in the placebo group.
- E. PACU LOS is shorter in patients receiving sugammadex as compared with placebo patients.
- F. Fewer patients in the sugammadex group have respiratory complications or require respiratory monitoring (O₂ desaturation, atelectasis, O₂ administration, CPAP, BiPAP, reversal medication).

	
 G. The sugammadex group has higher train-of-four (TOF) ratios than the placebo group at equivalent time points throughout their PACU stay. H. The ExSpiron is able to identify respiratory depression (defined as instances of MV <40% MV_{PRED} lasting at least 1 minute) occur prior to instances of SpO₂ <90% lasting at least 2 minutes). I. Lower MV measurements (corrected for total morphine equivalents administered) are correlated with lower TOF ratios.
--	--

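### Hypothesis G is about the TOF ratio, but the only between-arm TOF analysis is a yes/no test at 0.90, so the hypothesis as worded has no named test

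*Combined protocol and SAP*

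**What the plan says.** Hypothesis G (section 2.1) reads: "The sugammadex group has higher train-of-four (TOF) ratios than the placebo group at equivalent time points throughout their PACU stay". Secondary objective (a), in the Core Protocol section, is a separate aim and is already a yes/no question: "determine whether patients receiving sugammadex will have a normal TOF ratio (>0.90) indicative of full neuromuscular recovery in the PACU".

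Section 2.7 B handles TOF as follows:

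- **Item a** ("Using Fisher exact test, we will compare across the two groups the incidence of") includes a.viii: "Normal TOF ratio (>0.90) at equivalent time points in the PACU". Arrival and discharge are given as examples, and the list is left open.
- **Item b** ("Using 2-sample t-tests we will compare") covers average MV in two windows, PACU length of stay, pain scores and opioid dose. TOF is not listed.
- **Item f** ("We will use Pearson correlations and linear regressions, without regard to treatment group to compare") includes MV against TOF ratio. It uses the ratio as a number, but with the arms pooled.
- **Item e**, the multi-factor ANOVA, has an open list of dependent variables "as defined in each hypothesis, based on demographics to demonstrate group uniformity". TOF is not named.

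Under section 2.7 C, the hypotheses after A1 and A2 are tested only if both of those succeed, and are reported with and without Hochberg correction. Under section 2.5, TOF monitoring in the PACU continues until a ratio of 1.0 has been documented.

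**The concern.** G is a statement about the level of a continuous measurement. The analysis that would decide it treats 0.91 and 1.00 as the same result, and likewise 0.40 and 0.89. Two things follow.

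First, the plan yields no between-arm estimate in TOF-ratio units for a hypothesis expressed in those units, and does not say which result decides G within the Hochberg set.

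Second, dichotomising discards information. A Fisher test could be non-significant when the ratios do differ, and that result would be the only evidence available on G.

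The plan treats MV differently: each MV window has an incidence comparison (a.i, a.ii) and a comparison of averages (b.i, b.ii). Section 2.7 D itself remarks that comparing incidences generally takes more data. TOF gets only the incidence form.

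**Working it through.** **Inputs from the plan.** 150 per arm (2.5, 2.7 D); residual block in the PACU 35% (2.7 D), with up to 40% having TOF below 0.9 (2.2 C); a 5% difference with SD 12% (2.7 D); a TOF of 1.0 is normal (2.2 C).

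**Assumptions not in the plan.** Two-sided 0.05 with no Hochberg adjustment, no missing readings, and a normal latent TOF ratio with equal SD in both arms. In steps 2 and 3 the 5% and 12% are read as TOF-ratio units, although 2.7 D words them as incidence.

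**Step 1: the plan's residual-block sample size.** As a comparison of two means:

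n = 2(1.96 + 0.84)² × 12² / 5² = 2 × 7.84 × 5.76 = 90.3

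The t-based version gives 91.4, rounded up to the stated 92. As two proportions, 35% against 30%, the plan's own formula gives 2 × 0.325 × 0.675 × 7.84 / 0.05² = 1,376 per group. The stated 92 is therefore a two-means calculation, whereas TOF is tested by arm only as a proportion.

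**Step 2: the same inputs at 150 per arm.** A t-test for a difference of 0.05 with SD 0.12 has 94.9% power. Now cut at 0.90:

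- Placebo mean giving 35% below 0.90: 0.90 + 0.385 × 0.12 = 0.946.
- Sugammadex mean: 0.946 + 0.05 = 0.996.
- Share below 0.90 on sugammadex: Φ((0.90 − 0.996)/0.12) = Φ(−0.80) = 21.1%.
- Exact Fisher power, 35% against 21.1%: 72.9%.
- Loss: 94.9 − 72.9 = 22 points. At a 40% placebo rate it is about 20.

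**Step 3: ceiling at 1.0.** Simulating the same case with the ratio capped at 1.0 gives 90% (t), 92% (rank-sum) and 74% (Fisher). The loss is 16 to 18 points.

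**Step 4: varying the effect.** Fisher power is exact, by enumerating both binomials. Rank-sum power is simulated, with values rounded to 0.01 and capped at 1.0.

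| Below 0.90, placebo v sugammadex | Fisher | Rank-sum, SD 0.08 | Rank-sum, SD 0.12 | Loss (points) |
|---|---|---|---|---|
| 35% v 25% | 43% | 65% | 63% | 20–22 |
| 35% v 20% | 80% | 96% | 95% | 15–16 |
| 35% v 10% | about 100% | about 100% | about 100% | 0 |
| 35% v 5% | about 100% | about 100% | about 100% | 0 |
| 20% v 10% | 63% | 93% | 90% | 27–30 |
| 10% v 5% | 30% | 76% | 66% | 36–46 |

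The simulated values move by a point or two between runs.

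**The case against.** The best defence is that 0.90 is the protocol's own threshold. Objective (a) defines full recovery by it, section 2.2 C defines residual block by it, and a.viii shares with G the idea of equivalent time points, so it can be read as the sponsor's way of putting G into operation. This stands as a reason to keep a.viii. It does not make a test of a proportion a test of whether ratios are higher, and the plan never says that a.viii decides G.

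Item e might be thought to cover G through its open list. Its stated purpose is group uniformity by demographics, so it is not a treatment comparison.

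The second defence is about effect size. Section 2.2 expects sugammadex to reverse block completely. If so, the contrast at arrival is 35% against something near zero, and both tests have about 100% power. This stands: under the effect the authors hope for, no power is lost, and the case rests on the missing test and estimate.

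Third, G is gated behind A1 and A2, and the sample size was set on those. This also stands, and it limits the consequence.

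A reader might infer a far larger loss. With 5% against 1% below 0.90 and SD 0.08, Fisher has 40% power and the rank-sum 99%, a gap of 59 points. The documents do not support that as a headline. They give 35%, or up to 40%, and nothing near 5%. The scenario needs latent means of 1.03 and 1.09, above the normal value of 1.0, with about 68% and 87% of readings at the cap. Nor is it an upper bound, since other assumed rates and models give other figures.

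**Conclusion.** The point holds as a mismatch between a secondary hypothesis and its analysis: G is worded on the TOF ratio, and no named analysis compares that ratio between arms. This is a matter of reading the text and does not depend on any power figure.

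The power cost is secondary and conditional. At the plan's 35% rate it is roughly 15 to 22 points for a moderate effect. It is larger if fewer placebo patients fall below 0.90, and nil if sugammadex brings block to 10% or less. These figures rest on the shift model, the SD of 0.08 to 0.12 and the unadjusted two-sided 0.05 level. Because G is reached only after A1 and A2 succeed, its real chance of success is lower under either test.

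Item a.viii is not an error, and nothing here touches the primary or key secondary conclusion. The change is worth making because it is cheap and uses data already collected.

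**What to change.** In section 2.7 B, add a between-arm Wilcoxon rank-sum comparison of the TOF ratio at PACU arrival, with a Hodges-Lehmann difference and 95% CI. A rank test suits a ratio that piles up at 1.0. Name it as the single test of Hypothesis G and the one that enters the Hochberg set in 2.7 C.

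Report later time points as supportive. Because monitoring may end once 1.0 is documented, a comparison at discharge could otherwise contain only patients who had not recovered. State that patients whose monitoring ended at a documented 1.0 stay in the analysis at 1.0.

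Keep a.viii as the analysis of secondary objective (a).

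The cost is a few lines of SAP text and one extra test. If the drug's effect were confined to crossing 0.90, the rank test would be slightly less sensitive than the cut, but the cut would still be reported.
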